12.4.4 MISSING DATA

All statistical tests on the performance endpoints will be performed using only those subjects with available data required for endpoint analysis. No missing value imputation will be performed.

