5.2 PERFORMANCE ENDPOINTS

The following performance endpoint will be assessed when the investigation procedure is performed:

 Device technical success (successful delivery and deployment of one bioprosthesis with one delivery system)

The following performance endpoint will be determined when the subject is discharged from the hospital or 10 days post implant, whichever occurs first:

 Procedure success defined as device technical success followed by the absence of adverse events requiring device reoperation, requiring implantation of permanent pacemaker (with baseline sinus rhythm and no other conduction issues), or subject death

The following performance endpoints will be assessed at each scheduled follow-up visit:

- Improvement in NYHA functional class
- Hemodynamic performance (mean gradient, effective orifice area, regurgitation by echocardiogram).

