9.6 DEVICE REMOVAL / EXPLANT PROCEDURE

Subjects with device removal or explant will be followed as described in section 9.4 and section 9.5; however neither echocardiography nor blood tests will be performed after discharge, unless required to better assess subject's health status.

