12.4 PHASE II ANALYSIS

12.4.1 ANALYSIS POPULATION

The primary safety analysis will include all the enrolled subjects including those enrolled in Phase I. The performance analysis will include the subjects who survived at least 30 days post implant.

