12.4.3 PERFORMANCE ANALYSIS

The device technical success and procedure success will be summarized by counts and percentages.

Subjects will be analyzed according to the NYHA classification preoperatively, at 3 months and annually post implant for 5 years. The distribution (numbers of subjects and percentages) in the various NYHA classes will be tabulated at each follow-up interval.

Echocardiography data will be obtained preoperatively, at discharge (or 10-days post implant, whichever occurs first), at 6-months and at 1, 3, and 5 year follow-ups. Descriptive statistics for the continuous echo variables and change from baseline (e.g. mean, standard deviation, and range) will be categorized by time interval and size. Regurgitation data will be summarized using frequency at each severity level.

Improvement in regurgitation at one year will be analyzed via the Wilcoxon Signed-Rank test. Change at one year from baseline for all other hemodynamic outcomes will be analyzed using paired *t*-tests.

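### Subjects explanted for leak before one year drop out of the 1-year regurgitation result, which then describes only valves still in place

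*Combined protocol and SAP*

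**What the plan says.** Four parts of the protocol bear on this.

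- **Endpoint and test.** Section 5.2 makes regurgitation on echocardiogram part of hemodynamic performance, assessed at scheduled follow-up visits. Section 12.4.3 tabulates it by severity level and adds: "Improvement in regurgitation at one year will be analyzed via the Wilcoxon Signed-Rank test". The other hemodynamic changes at one year get paired t-tests.
- **Population.** Section 12.4.1: "The performance analysis will include the subjects who survived at least 30 days post implant". It has no separate rule for subjects whose valve is later explanted.
- **Echo after explant.** Section 9.6 keeps subjects with removal or explant in follow-up, but "neither echocardiography nor blood tests will be performed after discharge, unless required to better assess subject's health status".
- **Missing data.** Section 12.4.4: "All statistical tests on the performance endpoints will be performed using only those subjects with available data required for endpoint analysis". It continues: "No missing value imputation will be performed".

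No section gives explanted subjects a regurgitation outcome, shows them as a category in the table, or plans a sensitivity analysis for them.

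**The concern.** The missing 1-year echo is not a random gap. It is produced by the protocol's own follow-up rule, and for a valve explanted because it leaked the reason for the gap is the outcome being measured. The subjects with the worst result on this endpoint are the ones without a value.

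This matters more here than in many device studies. The stated purpose (section 2.2) is to confirm that the balloon-expandable frame does not harm safety or performance. Section 2.3.1 says that the cloth on the frame is there to help prevent paravalvular leak, and section 3.3 gives the potential advantage as fewer sutures without added leak risk. Section 3.1 lists leak that needs intervention or reoperation as a possible risk of this device. The trial has a single arm, so no comparator passes through the same selection. A reader of the 1-year table would see a distribution conditional on the valve still being in place, and no text requires the table to say so.

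**Working it through.** **Following one subject through the plan.** Take a subject who survives 30 days and whose valve is explanted for leak at, say, month 6.

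1. Section 12.4.1: the subject survived 30 days, so is in the performance population.
2. Section 9.6: the subject stays in follow-up, but normally has no further study echo. An echo done under the health-status exception would no longer show the intact study valve, and the plan does not say whether it would be used.
3. Section 12.4.3: the signed-rank test needs a baseline and a 1-year grade. There is no 1-year grade for the study valve, so there is no pair and no entry in the 1-year table.
4. Section 12.4.4: no imputation, so the subject is left out.

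Echoes before explant (discharge or day 10, and later visits reached with the valve in place) still enter the tables for those visits.

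**Is there a planned figure to reproduce?** No. The documents give no alpha, power, effect size, regurgitation rate or explant rate for these tests. The only related arithmetic is enrolment, 10 + 340 = 350, which agrees.

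**Illustration 1: the severity table.** Assumptions, none from the documents: 320 subjects have a 1-year echo, 4 of them show moderate or worse regurgitation, and k others were explanted for leak before the visit.

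Rate with explants counted = (4 + k) / (320 + k)

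| k | Share of 350 enrolled | Rate | Ratio to 1.25% |
|---|---|---|---|
| 0 | 0% | 4/320 = 1.25% | 1.0 |
| 4 | 1.1% | 8/324 = 2.5% | 2.0 |
| 10 | 2.9% | 14/330 = 4.2% | 3.4 |

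**Illustration 2: other assumptions.** Let k of 350 be explanted before one year, all for leak, and let every other subject have an echo. If about 1% of those echoed have significant regurgitation, the available-case rate stays near 0.9% whatever k is, while the rate with explants counted climbs:

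- k = 4: 3/346 = 0.87% against 7/350 = 2.0%
- k = 10: 3/340 = 0.88% against 13/350 = 3.7%
- k = 18: 3/332 = 0.90% against 21/350 = 6.0%

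If about 2% of those echoed have it, the available-case rate runs from 7/346 = 2.02% (k = 4) to 7/332 = 2.11% (k = 18), against 11/350 = 3.1% to 25/350 = 7.1%.

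**Illustration 3: the signed-rank test.** Assumed shares for grades 0 to 4: baseline 0.35, 0.35, 0.20, 0.07, 0.03 (mean 1.08); one year with the valve in place 0.55, 0.33, 0.10, 0.015, 0.005 (mean 0.595).

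- Mean improvement with the valve in place = 1.08 − 0.595 = 0.485 grade.
- Giving a share s of subjects grade 4 lowers it by s × (4 − 0.595) = 3.405 s.
- s = 4/350: a drop of 0.039. s = 18/350: a drop of 0.175, to 0.310.

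A simulation of 300 trials of 350 at each explant share agrees: 0.477 falls to 0.438 with 4 explants, and 0.485 falls to 0.310 with 18. The median p-value moves from about 1 × 10⁻¹⁰ to 3 × 10⁻⁹ with 4, and from about 1 × 10⁻¹⁰ to 3 × 10⁻⁵ with 18. The estimate moves; the significance does not.

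**The case against.** The strongest reply is that the failures are reported, only elsewhere. Paravalvular leakage is a primary safety endpoint, and valve-related reoperation and explant are further safety endpoints (section 5.1). Section 12.4.2 gives leakage early percentages, late linearized rates and Kaplan-Meier freedom from event; the other complications get early percentages and linearized rates. The primary safety analysis covers all enrolled subjects. On this view, hemodynamics of the valve in place, with explants shown separately, is a coherent descriptive target, and a worst-level rule turns it into a composite that counts one event in two places.

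Much of this stands, and it rules out several stronger readings that a reader might infer:

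- *That failed valves disappear from the trial.* They do not; they are in the safety results.
- *That these subjects never appear in any regurgitation table.* They appear at visits before explant.
- *That every reoperation for leak is lost.* Section 9.6 stops echo only after removal or explant. A subject reoperated with the study valve kept still has the 1-year echo.
- *That the trial's conclusion is at risk.* Section 2.2.1 ties Phase II success to a data monitoring committee judgement on 3-month data, and no performance goal is attached to 1-year regurgitation. The test compares the native valve before surgery with the prosthesis, so the contrast is probably large.
- *That every explant is a regurgitation failure.* Explants for endocarditis or thrombosis, for example, need not be.

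The objection does not remove the point. Section 12.4.1 puts these subjects in the performance population, and no section limits the 1-year result to valves still in place. If that is the intended target, the plan should say so and show who is left out. Nor is a measurement being invented: explant is a recorded event, and section 11.3.2 has its cause determined.

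**Conclusion.** The point holds, within limits. As written, the 1-year regurgitation table and signed-rank test omit 30-day survivors whose study valve was explanted for leak or regurgitation before that visit. The omission depends on the outcome and favours the device.

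Its size cannot be derived from the documents. With 4 to 10 such explants and 4 of 320 echoed subjects affected, all assumed, the rate of moderate or worse regurgitation would be 2.0 to 3.4 times the available-case figure. With no such explants the bias is nil. The severity distribution and the estimated improvement are what change. The test's significance, and the committee's decision on success, would probably not.

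This is worth correcting because the stated population and the analysed set differ on the feature that the frame is meant to protect. It is not a flaw in the safety reporting.

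**What to change.** In sections 12.4.3 and 12.4.4:

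1. Count subjects explanted for study-valve leak or regurgitation before the visit at the worst regurgitation level, on a separately labelled row of the 1-year frequency table and in the signed-rank test.
2. Show the result for valves still in place beside it, labelled as such.
3. Limit the rule. It does not apply to subjects reoperated with the study valve kept, to intra-operative removals (which bear on device technical success), or to explants for other causes. Where a study-valve grade was observed at the visit, use it.
4. For all echo variables, report the number missing at each visit by reason: death, explant, missed visit. Continuous variables stay on observed data.

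The cost is a change of wording in the statistical section. The events and causes are already recorded, and no new procedure is needed. The downside is a slightly less favourable regurgitation figure.

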13 MONITORING

13.1 MONITORING METHODS

The Investigation Sponsor will assign a monitor to monitor the progress of the clinical investigation at each investigational center. The monitor will remain in close contact with each investigational center throughout the duration of the investigation to provide any needed materials, (i.e. investigation forms) or answer any questions. The monitor will be responsible for verifying that the subject signed the consent, reviewing date recorded on the eCRFs, and visiting each investigational center periodically to observe investigation progress and compliance with clinical protocol and regulations applicable to this clinical investigation.

Monitoring visits will be scheduled throughout the duration of the clinical investigation between the monitor and the principal investigator at a mutually convenient and available time. These visits will assure that the facilities are still acceptable, the protocol and investigational plan are being followed, the EC is notified of approved protocol changes as required, complete records are being maintained, appropriate timely reports have been made to the Investigation Sponsor the EC and the Competent Authority (as applicable), device and device inventory are controlled and the investigator is carrying out all agreed activities. Any personnel changes must be reported to the monitor immediately and a training program scheduled and documented. Additionally, the monitor will do source data verification to assure CRF data accuracy and completeness. The scope of monitoring is defined and will be conducted in accordance with the TRITON Study Monitoring Plan.

To protect subject confidentiality, the subject's name must not appear anywhere on the imaging media sent prepared for evaluation by the core lab, or supporting documentation removed from the investigational center. Each page should be identified with the subject's ID number only. All other subject identifiers (i.e., medical record number, personal number) are to be obscured.

13.2 MONITORING PLAN

Prior to subject enrollment, an initiation visit will be completed at each investigational center to ensure the following:

- 1. Ethics Committee and applicable regulatory body approvals have been obtained and documented,
- 2. The investigators and clinical investigation personnel are appropriately trained and clearly understand the investigation,
- 3. The investigators and clinical investigation personnel accept the obligations incurred in undertaking this clinical investigation.
- 4. The Delegation of Authority form has been completed properly

Periodic monitoring visits will be made at all enrolling investigational centers in accordance with center enrollment rates. Investigation centers should be visited a minimum of once each year by the monitor.

Upon termination or conclusion of the clinical investigation, the monitor will perform a close-out visit.

Monitoring activities are further described in the TRITON Study Monitoring plan for this investigation.

13.3 PROTOCOL DEVIATION

A protocol deviation is defined as an event where the Investigator or investigation personnel did not conduct the investigation according to the clinical protocol or the Clinical Investigation Agreement.

Deviations shall be reported to the Investigation Sponsor regardless of whether medically justifiable or taken to protect the subject in an emergency. Subject specific deviations and non-subject specific deviations, (e.g. unauthorized use of an investigational device outside the investigation, unauthorized use of an investigational device by a physician who is not listed in the Clinical Investigation Agreement, etc.) will be reported in writing. Investigators will also adhere to procedures for reporting investigation deviations to their EC in accordance with their specific EC's reporting policies and procedures.

For reporting purposes, deviations are classified as major or minor:

- 1. Major deviations:
 - a. Any deviation from subject inclusion and exclusion criteria;
 - b. Any deviation from subject informed consent procedures;
 - c. Unauthorized use of an investigational device outside the investigation;
 - d. Unauthorized use of an investigational device by a physician who is not listed in the Clinical Investigation Agreement.
- 2. Minor deviations:
 - a. Deviation from a protocol requirement such as incomplete/inadequate testing procedures (unless procedure is optional or deemed medically inadvisable to perform on subject);
 - b. Follow-up performed outside specified time windows.

13.3.1 EXCEPTIONS

Some information in this investigation is collected for Investigation Sponsor research purposes and is therefore not a reportable protocol deviation if absent.

At Baseline this includes:

- Blood pressure
- Pre-operative risk scores
 (Additive euroSCORE, Logistic euroSCORE, STS risk score)
- Type of medication currently in use (ACE or ARB Inhibitors, ADP inhibitors, Antiarrhythmics, Anticoagulants, Antiplatelets, Beta Blocker, Glycoprotein IIb/IIIa inhibitor, Inotropes, Lipid Lowering, Nitrates, or Steroids)

During the investigation procedure this includes:

- Surgical approach
- Suture technique
- Debridement procedure
- Surgical procedure timing
- Device procedure timing
- Inflation device used
- Balloon inflation pressure and number of inflations
- User assessment: device ease of use

At hospital discharge this includes:

- Blood pressure
- Subject discharged to: home, another hospital, extended care
- Current medications
- Post-operative hospitalization (time in intensive care unit, intermediate care, general ward)
- Ventilation time
- Post-operative blood replacement, including Cell Saver amount auto transfused (in intensive care unit, intermediate care, general ward)

At follow-up evaluation this includes:

- Visit type (Hospital/Clinic, In-patient admission, phone)
- Current medications

13.4 COMMUNICATION PROCEDURES

During the course of the clinical investigation, all correspondence (letters, telephone call, emails and faxes) regarding the investigation must be maintained in the investigation binder provided by the Investigation Sponsor. This binder must be made available for monitoring visits or audits.

14 COMMITTEES

14.1 DATA MONITORING COMMITTEE

The Investigation Sponsor will appoint a Data Monitoring Committee (DMC) whose members will be independent of both the Investigation Sponsor and the Investigators. The role and composition of the DMC is described in the DMC Charter for this clinical investigation.

14.2 CLINICAL EVENTS COMMITTEE

The Investigation Sponsor will appoint a Clinical Events Committee (CEC) whose members will be independent of both the Investigation Sponsor and the Investigators. The role and composition of the CEC is described in the CEC Charter for this clinical investigation.

15 ETHICAL AND REGULATORY CONSIDERATIONS

15.1 APPLICABLE REGULATIONS AND GUIDELINES

The clinical investigation will be conducted in compliance with the regulations set forth in Table 8. It is the responsibility of the investigator(s) and Sponsor to comply additionally with country specific regulations.

· · · · · · · · · · · · · · · · · · ·	
Region	Regulation / Guideline
Europe	- 2007/47/EC European Medical Device Directive (MDD)
	- ISO 14155:2011 (Clinical investigation of medical devices for human
	subjects – Good clinical practive)
	- ISO 5840: 2005 (Cardiovascular implants-Cardiac valve prostheses)
	- Declaration of Helsinki
	- ISO 14971:2007 (Medical Devices – application of risk management to
	medical devices)

Table 8: Applicable Regulations and Guidelines

Furthermore, the investigator will use as guidance pertinent sections of ICH E6 GCP or will comply with the laws of the applicable country, whichever will afford greater protection to subjects screened for participation in the clinical investigation and subjects who participate in the investigation.

Principles protecting the rights, safety and well-being of human subjects, which are the most important considerations and shall prevail over interests of science and society, shall be understood, observed, and applied at every step in the clinical investigation.

15.2 IMPROPER INFLUENCE

The Sponsor shall avoid improper influence on, or inducement of, the subject, monitor, any investigator(s) or other parties participating in, or contributing to, the clinical investigation. The Investigators shall avoid improper influence on or inducement of the subject, sponsor, monitor, other investigator(s) or other parties participating in or contributing to the clinical investigation

15.3 DATA PROTECTION AND SUBJECT CONFIDENTIALITY

The Investigation Sponsor is dedicated to maintaining the confidentiality and privacy of subjects who volunteer to participate in the clinical investigation. Passwords are issued to appropriate personnel to insure confidentiality and protection of the database by allowing variable levels of access to the computer system. In addition, the principal investigator is responsible for maintaining confidentiality throughout the clinical investigation. The hard copies of the source documentation are to be maintained in a secure area with limited access. All subject identifiers will be obliterated from all photocopies of source documents that have been removed from the investigational center. Subject identifiers include, but are not limited to: subject's name, social security number or equivalent, and medical / hospital number. All documents for the clinical investigation will identify the subject by a subject identification number assigned by the Investigation Sponsor.

15.4 INFORMED CONSENT AND REVIEW COMMITTEES

All subjects must provide written informed consent in accordance with the local investigational center's EC rules and regulations. A copy of the consent form from each center must be forwarded to the Investigation Sponsor for review and approval prior to submitting it to the institutional review committee. Each center must provide the Investigation Sponsor with a copy of the investigational center's EC approval letter (stating at a minimum, the clinical investigation name or identification number, protocol revision being approved and an approval date) and the informed consent prior to the initiation of enrollment at that center. If yearly approvals for the continuation of the investigation at each investigational center are required, they must also be forwarded to the Investigation Sponsor.

If national or regional EC requirements are less strict than the requirements of ISO 14155:2011, the Sponsor will apply the ISO14155:2011 requirements to the greatest extent possible, irrespective of any lesser requirements, and shall record such efforts.

15.5 INVESTIGATOR RESPONSIBILITIES

15.5.1 GENERAL DUTIES

The investigator shall ensure that all work and services described herein, or incidental to those described herein, shall be conducted in accordance with the highest standards of medical and clinical research practice and the applicable regulations. The investigator shall be responsible for the day to day conduct of the clinical investigation and for the safety and well-being of human subjects enrolled. The investigator will provide copies of the current clinical protocol to all staff responsible for conduct of the clinical investigation.

The principal investigator is responsible for obtaining EC approval to start the clinical investigation at his/her investigational center.

If there is a change or addition of co-investigator, an amended Clinical Investigation Agreement must be completed promptly.

15.5.2 INVESTIGATOR RECORDS

The principal investigator will maintain the accurate, complete, and current records relating to participation in this clinical investigation. Records including eCRFs and supporting data including hardcopies of all blood and diagnostic exams, signed Clinical Investigation Agreement, protocols and protocol amendments, signed informed consents, use of devices, EC approval letters, EC submissions, correspondence, including required reports and other documents pertaining to the conduct of the clinical investigation must be kept on file by the investigator. If the investigator(s) wishes to assign the files to someone else or remove them to another location, he/she should consult with the Investigation Sponsor in writing as to this change. Files for the clinical investigation must be maintained in a known location until the Investigation Sponsor notifies the investigator in writing that he/she may discard them.

